#### **Analysis of heterogeneity of treatment effects (HT-1, HT-3, HT-4)**

We will explore the differential effects of the intervention on patient subgroups defined by factors known or hypothesized to have associations with poorer TBI outcome: facility vs. community discharge, minority race/ ethnicity, older age, male gender, lack of or lower degree of caregiver

involvement, greater severity of TBI, presence of pre-injury psychosocial limitations (e.g., unemployment, substance abuse) and medical or psychiatric comorbidity, as well as study site, resource variability and insurance type. These factors will be entered in a single linear regression model in addition to the intervention group, using PART-O-17 as the response variable. Before constructing the model, we will assess whether the explanatory variables are correlated to each other. When two or more variables are deemed highly correlated, to avoid problems with collinearity, we will construct the model with the variable that provides the best model (from fit and diagnostic tests). From previous research, we hypothesize that severity of TBI and presence of pre-injury psychosocial limitations will interact with the intervention group, and those interactions will be included in the model. With our expected sample size we anticipate being able to address these questions.

### **Data Management (IR-2, MD-1)**

The database will be developed by the National Data and Statistical Center (NDSC) at Craig Hospital which has the existing infrastructure and IRB-approved clearances to accept both civilian and VA data for the TBIMS program. Only registered TBIMS users will be assigned a password to access the database for online data entry. Once data collection is complete, study information (recruitment and screening outcome, basic demographic information, data collected to test study hypotheses) will be entered with a participant's study ID, i.e. not name into a password protected NDSC database accessible via secured-internet connection.

Site-specific identifiable information such as name, address, medical record number, email or phone numbers will be stored on a secure server at each site in a password-protected database separate from study data. Study data that will be used for data analysis purposes will be stored separately on a restricted access server managed by the NDSC. We will maintain a link between the identifiers and study data via use of a unique subject identification number. The crosswalk between identifying information and the subject identification number will reside in the password-protected databases on a secure server at each site only accessible by study personnel.

There are a few exceptions to the separation of identifiers and study data as described above. One exception is street address, which will be collected at each time point and stored with identifying information on a secure server at each local site for contact purposes AND on a restricted access server at the NDSC at the Craig Hospital.

Another exception, as described above, will be the audio recordings of contacts between the patient and/or caregiver participants and the TCM. The audio recordings will be labeled with the subject's identification number. The only identifying information that will be contained in each recording will be the participant's voice and if the TCM or other parties state the participant's name during the contact. These recordings will be kept on a secure server of the NDSC which can only be accessed by study personnel.

Also, some data regarding "process variables" collected by the study TCMs during contacts with participants in the RTP group, e.g. time on phone calls, resources provided to subjects, basic needs assessed, etc., will be stored with some identifying information in the password-protected TCM database on a secure local server. These data will eventually be sent to the NDSC with subject identification number only for permanent storage.

Finally, certain dates that may identify subjects (e.g. date of birth, date of injury, date of admission) will also be obtained and entered into the NDSC database along with other study data.

Study databases will be automatically linked to existing TBIMS databases with demographic, injury severity, and rehabilitation outcome data collected as part of the TBIMS infrastructure. Study researchers will create a crosswalk between the BRITE ID number and original TBIMS ID number for all participants enrolled in both studies to allow for merging of the data between the proposed study and TBIMS data elements. Project investigators will audit all data entry prior to final submission as part of routine TBIMS study procedures. The database sits behind a Cisco ASA 5520 firewall on a separate Microsoft SQL 2013 Server and will utilize whole database encryption technology using NetLib Encryptionizer (FIPS 140.2 compliant). All local information security practices will be implemented.

Due to HIPAA and Institutional Review Board (IRB) guidelines, any personal identifying information transmitted from the participant to the research office needs to remain private and confidential. As a result, personal identifiable information (PII) of patients approached/enrolled at each study site used for contacting and tracking participants will be stored locally in a password-protected database on a secure server at each site.

To ensure data quality and minimize missing data, data collectors will be trained and tested on established criteria on both medical record abstraction and the measures used in the follow-up interview. In addition several levels of data checks will be implemented. First, when data collectors enter data into the web based data entry program they will be notified which fields have been skipped. In general all fields, with the exception of some text fields, will have valid codes associated with them, so no true blank variables should exist in the database. Furthermore, when appropriate, skip patterns will exist for some variables, which can automatically populate variables that would then be considered "not applicable". The data entry program will also not allow an entry that isn't considered valid mostly through the use of drop down controls in which only valid answers are presented.

Second, while data is being entered there will be a process for a data collector to run various data checks like logical errors (e.g. injury date occurring before birth date) or data inconsistencies (e. g. currently working, but hours of work past week = 0) can be programmed into the system to alert the data collector to variables that need attention. Above and beyond the notifications of errors and missingness that occurs while a data collector is entering data, all authorized people of the study can run real time reports that reflect not only missingness by variable, but missingness by person as well. Missing data reports will be reviewed on a quarterly basis by staff at the NDSC as well as coordinators at each site. The success of the data quality management methods used by the TBIMS is demonstrated in the low levels of missing data typically observed. Among TBIMS participants in the 2012-2017 funding cycle, 94% completed their 1 year interview and of those, <3% had missing PART-O-17 data. We would anticipate similarly low rates of missing data with the current study (**MD-1**).

## REPLICATION AND REPRODUCIBILITY OF RESEARCH AND DATA SHARING

Procedures for the current study will be carefully documented in a Manual of Procedures (MOP) document which will be created at the start of the project and updated as needed throughout the project period. Adherence to the MOP will be regularly monitored by the lead site, and each site PI will ensure adherence to the SOP at their study site. As described above, RDP is already being performed at all study sites and will be documented during the study. Likewise, the RTP protocol will be carefully delineated in the MOP to ensure the same core ingredients are implemented across sites. By using a detailed MOP and documenting procedures in such a way

that they can be followed uniformly across 6 study sites, it will be possible for other investigators to replicate the findings of the current study. Most importantly, it will be possible for other clinical teams to replicate the discharge planning protocol that is associated with optimal outcomes.

The MOP will include: (1) an overview of the study, including background information, study aims, and hypotheses to be tested; (2) a step-by-step description of recruitment procedures, including procedures for initial contact with potential participants, for determining participant eligibility (inclusion and exclusion criteria), and for tracking potential participant flow; (3) procedures for the informed consent process; (4) participant scheduling procedures; (5) randomization procedures; (6) outcome assessment protocols, including timing of assessments, detailed descriptions of all of the measures; (7) treatment procedures and logistics; (8) strategies for handling participants who drop-out or are unable to be contacted for treatment or outcome assessments; (9) a rationale for and strategies to ensure outcome assessors remain unaware of participants' group assignments; (10) general telephone procedures and etiquette; (11) data entry procedures, including rules for handling of missing data; (12) data management (data definitions, scoring syntax, coding instructions) and planned analyses procedures; (13) participant flow tracking procedures (CONSORT); (14) the location of facilities, forms, and materials; (15) strategies for handling and recording protocol deviations; (16) the data safety monitoring plan; (17) a plan for handling emergent situations (e.g., suicidal ideation in a study participant); and (18) procedures for maintaining Human Subjects approvals. Once Human Subjects approval is granted at each site, a log of all Human Subjects protocol changes and approvals will be kept as a supplement to the MOP. We will also include a tracking log of decisions made throughout the study that will be contained within the MOP.

Additional sections will be included in this study's MOP. The manual will include a section describing the Stakeholder Engagement Plan, which will include a list of all stakeholders and investigators, a governance plan, and a detailed description of the plan itself (e.g., engagement activities, frequency, and type). A final copy of the manual will be available to the public on our study website within six months of the end of Year 5.

### **Data Management and Data Sharing**

Study investigators will comply with PCORI's policy for data management and data sharing. Specifically, investigators will make available at the end of the study the following: (1) a full data package which includes a final clean and locked data set containing all the data used in the analyses described in the PCORI final research report; (2) the study protocol including descriptions of study design, procedures and full statistical analysis plan (including all amendments); (3) data dictionaries; and (4) any analytic code used. The study protocol will be submitted to the sponsor as a deliverable, whereas the remaining items will be deposited into a PCORI-designated repository. Study investigators will participate in a Data Contributor Agreement (DCA) with the PCORI-designated repository by the date when the study investigators submit the draft of the final research report to PCORI. The data set must be provided to the repository by the date the final research report is accepted by PCORI. The data will then become available to outside researchers when the final research report is uploaded to the PCORI website, or when the primary paper for the study has been published in a peer-reviewed journal, whichever comes first. Subsequently an independent committee representing the repository will review requests for the data by researchers outside the study.

Specific details regarding PCORI's policy for data management and sharing here:

## **Location of Facilities, Forms, and Materials**

### *Facilities*

The six TBIMS sites involved in the current project (University of Washington, Indiana University School of Medicine/Rehabilitation Hospital of Indiana, Moss Rehab Hospital, Baylor Institute for Rehabilitation, Ohio State University Wexner Medical Center, and Mount Sinai Health System (NY)) will enroll participants and collect primary data for this project. The TBIMS infrastructure with its demonstrated history of successful enrollment and research infrastructure is well positioned to participate in this project. All subcontracted organizations have had extensive experience in the TBIMS highlighting organizational support for TBI rehabilitation research. Investigators at each of these locations have already been identified and are identifying all eligible members of the target population and enrolling the majority who meet the eligibility criteria into TBI rehabilitation research projects.

In addition to participating in the primary research data collection, the Traumatic Brain Injury Model Systems National Data and Statistical Center at Craig Hospital, CO, will manage data collected using established data management and quality standards.

The six TBIMS sites agree that any Confidential Information obtained that is protected health information (PHI) of a patient will be kept confidential pursuant to the Standards for Privacy of Individually Identifiable Health Information at 45 CFR Parts 160 and 164 ("Privacy Rule") and all other applicable federal, state, and local laws, statutes and regulations, as well as each sites own internal rules and regulations governing the confidentiality of patient records and information.

### *Forms*

The case report forms will follow guidelines set forth by the NDSC to align with the database. Access to the paper CRFs /eCRFs will be limited to personnel directly participating in the study. Data should be entered into the CRFs/eCRFs completely by examining personnel or the study coordinator. The CRFs/eCRFs must be completed as soon as possible after any subject evaluation or communication.

Copies of the most recent CRFs are located on the BRITE website in the 'Study Materials' folder under the 'SOP' tab.

**Security of records:** The following protocol will be used to ensure the security on non-electronic study documents: a) Signed consent forms will be stored in a locked filing cabinet in a non-public area; b) All confidential documents that are disposed of will be placed in a locked confidential document-recycling container; c) All electronic identifying information will be stored in separate files from other data; and d) All files will be password protected and stored on a secured and restricted server.

Please see the “Data Management” section above for a listing of exceptions to the separation of identifiers and study data as described above.

#### *Materials*

Portions of medical charts will be reviewed to determine participant eligibility. These procedures will be approved by IRBs at all sites for TBIMS and meet HIPAA regulations. Once informed consent takes place, additional data regarding the injury will be gathered from the medical record including severity and cause of injury, demographic information (such as age), and comorbid diagnoses. All data obtained from participants or their proxies will be collected via interviews (either in person or over the phone).

The interviews will contain questions about current and past psychiatric history, current mood, post TBI symptoms, and need for assistance. Study data will be stored at the TBI National Data Center while all identifying personal contact and/or health information will be stored at each local site. These data will be linked via study code number and research staff will have access to participant identities.

#### *Pertinent Websites*

##### National Data and Statistical Center Main Support Website:

<https://www.tbindsc.org/Contact.aspx>

This website serves as the portal for all data collected for the TBIMS study, as well as basic SOPs pertaining to TBIMS.

##### National Data and Statistical Center BRITE Study Website:

<https://brite.tbindsc.org/Default.aspx>

This website serves as the portal for all data collected specifically for the BRITE study. It also houses all study materials, study protocol, and MOPs pertaining to TBIMS.

## SAFETY MONITORING

### **Adverse Event and Serious Adverse Event Information: Definitions**

#### *Adverse Event*

An adverse event (AE) is any untoward medical occurrence in a participant during participation in the study regardless of randomization assignment. An adverse finding can include a sign, symptom, abnormal assessment (laboratory test value, vital signs, electrocardiogram finding, etc.), or any combination of these. Staff will document any occurrence that:

- 1) meets the definition above;
- 2) is a new symptom/condition for the participant, OR a symptom/condition that began before enrollment yet has become significantly worse following enrollment; and
- 3) results in or warrants treatment by a health care provider.

The relationship between the event and study procedures will be determined by research staff. Research staff will be instructed to seek counsel from study investigators if the relationship is unclear.

#### *Serious Adverse Event (SAE)*

A serious adverse event (SAE) is any AE as described above which results in one or more of the following outcomes:

- Death
- A life-threatening event
- Inpatient hospitalization or prolongation of existing hospitalization
- A persistent or significant disability/incapacity that began following enrollment
- A congenital anomaly or birth defect
- An important medical event based upon appropriate medical judgment

An AE is also considered serious when medical, surgical, behavioral, social or other intervention is needed to prevent such an outcome.

We do not document a planned surgery as an AE UNLESS the surgery stems from an acute untoward medical occurrence, i.e. surgery as an intervention to prevent a worse outcome based on the acute occurrence. Also, we will document a planned surgery if there are complications from the surgery that require hospitalization. In this scenario, the complications rather than the surgery itself is the SAE, but we will document the surgery as the primary factor that contributed to the SAE.

Any unplanned surgery will still be documented as an adverse event.

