## **ABSTRACT**

### ***Background and Significance:***

Each year about 2.8 million people sustain a traumatic brain injury (TBI) in the US, and at least 25% of these injuries are classified as moderate to severe. Nearly half of those hospitalized for TBI have long-term disability. The majority experience psychological, physical, social, or vocational problems, many of which become chronic. TBI outcomes are affected by the type, location and severity of injury and are impacted by the availability, expertise, and intensity, duration, and timing of rehabilitation treatment. Following inpatient rehabilitation, Interventions for TBI-related symptoms and impairments are not consistently delivered to those in need and individuals are challenged to manage their own care because of the nature of their brain injuries (e.g., poor memory, behavioral problems, social isolation). Community resources are limited and primary care providers are unprepared to care for TBI-related problems, leaving many TBI survivors with unmet healthcare needs. There is a dearth of comparative effectiveness research examining patient-centered approaches to overcome the personal and organizational barriers to receipt of appropriate care. Current clinical practice guidelines prescribe hospital-based education, reassurance, advice, and referral after TBI. Given the heterogeneity in severity and range of problems, more assistance following discharge may be required to improve outcomes. Recently, models that use (1) telehealth to reduce barriers to care and (2) case management to improve coordination of care have been found to be acceptable and effective in improving quality of life after TBI. Therefore, we plan to compare the effectiveness of Standardized Discharge Care (SDC) as labeled in our original application and grant proposal, henceforth referred to as the "Rehabilitation Discharge Plan" (RDP), vs. RDP plus Optimized Transition Care (OTC) as labeled in our original application and grant proposal, henceforth referred to as "Rehabilitation Transition Plan" (RTP) in improving patient-centered outcomes in people with recent moderate to severe TBI.

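### The SAE disability criterion covers only disability that began after enrollment, while the AE rule also counts significant worsening, so lasting worsening of an existing disability can be graded non-serious or graded inconsistently

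*Combined protocol and SAP*

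**What the plan says.** Under Safety Monitoring, the Adverse Event section tells staff to document an untoward medical occurrence that is new, "OR a symptom/condition that began before enrollment yet has become significantly worse following enrollment". The occurrence must also meet a treatment condition: it "results in or warrants treatment by a health care provider".

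The Serious Adverse Event (SAE) section builds on that definition: "A serious adverse event (SAE) is any AE as described above which results in one or more of the following outcomes". Six outcomes follow. The disability outcome reads "A persistent or significant disability/incapacity that began following enrollment". It is the only one of the six with a limit on when it began. Two others matter here: "Inpatient hospitalization or prolongation of existing hospitalization" and "An important medical event based upon appropriate medical judgment". A further sentence adds a preventive route: "An AE is also considered serious when medical, surgical, behavioral, social or other intervention is needed to prevent such an outcome".

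The grade decides the reporting path. SAE Reporting and Documentation gives unanticipated SAEs related to study procedures (other than fatal or life-threatening ones, which go to all parties at once) 24 hours to the site and lead-site principal investigators, one week to the DSMB chair, and 5 business days to database entry. Anticipated or unrelated SAEs have one month to entry and go into the bi-annual and annual reports. AE Documentation also gives plain AEs one month.

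**The concern.** The SAE definition takes in every AE, including AEs that are worsened pre-existing conditions. Its disability outcome then carries only the first half of the AE rule (new) and not the second (worse). The revision history for version 8.0 records the AE wording on worsening. No matching change to the SAE outcome is logged.

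The population makes this more than a drafting detail. Participants are recruited during inpatient rehabilitation for moderate-to-severe TBI, and the Abstract says: "Nearly half of those hospitalized for TBI have long-term disability". That is a statement about hospitalized TBI in general, not a measured rate for this trial. Even so, disability at enrollment should be common, and a lasting harm may well appear as worsening.

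Two things depend on the grade. One is the speed of reporting for related, unanticipated events. The other is the SAE count. The DSMB compares events between arms, and adverse effects of RTP are a stated ground for stopping the study. The AE Attribution Scale foresees related events arising from strategies prescribed in case management sessions, which only RTP participants receive. The SAE count should therefore not depend on how each site reads one phrase.

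**Working it through.** No arithmetic applies. The check sets the two definitions side by side, runs four cases through them, and then compares the reporting paths.

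**Step 1: the two rules**

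| Situation | Adverse Event section | SAE disability outcome |
|---|---|---|
| New after enrollment | Counted, if treated or warranting treatment | Counted, if persistent or significant |
| Present before, significantly worse after | Counted, if treated or warranting treatment | Not mentioned |

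**Step 2: cases**

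- **A. New disabling deficit after enrollment.** It meets the disability outcome and is serious.
- **B. Mild deficit at enrollment that later becomes lastingly disabling.** The symptom predates enrollment, but the significant disability arguably began afterwards. The text supports either grade.
- **C. Significant disability at enrollment that becomes lastingly worse, managed without admission or threat to life.** The disability did not begin after enrollment, so read literally the outcome is not met.
- **D. As C, but with an admission, a threat to life, or an intervention needed to avert either.** It is serious by another route, and none of those routes has an onset limit.

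**Step 3: does any other text bring in case C?** The preventive sentence points back to the listed outcomes. For disability it inherits the same onset limit; for hospitalization and threat to life it does not, which is why case D is covered. The remaining route for C is the important-medical-event outcome, which rests on judgment. Appendix 2 (Problems Reports) repeats the reporting rules without redefining seriousness. No section extends the disability outcome to worsening.

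**Step 4: what the grade changes**

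| Event | If an SAE | If a plain AE |
|---|---|---|
| Unanticipated and study-related | Site and lead-site PIs in 24 hours; DSMB chair within one week; entry in 5 business days | Entry within a month; internal review quarterly; external review bi-annually |
| Anticipated or unrelated | Entry within a month; internal review quarterly; external review bi-annually | The same |

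The first row therefore changes timing and the second changes only the label. The first row also has a partial safeguard. If the event meets the unanticipated-problem definition, it is entered within 5 business days and the DSMB chair is contacted within one week whatever its SAE grade. That definition requires the event to be unexpected, at least possibly related, and suggestive of greater risk than was previously known. The 24-hour deadline in that section is stated for serious unanticipated problems.

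**The case against.** The strongest reply is that the two sections date different things. The AE rule dates the symptom or condition; the SAE outcome dates the resulting disability. Worsened conditions already enter the SAE definition as AEs, and the onset limit has a sensible purpose: it stops baseline TBI disability from making every AE serious. On that reading, a mild hemiparesis that becomes permanently disabling qualifies, because the disability came after enrollment. This stands for case B as a reasonable reading, though not the only one. It does not settle case C, where disability was already present and deepened. The AE section states worsening separately where it means to include it.

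A reader might also infer that lasting worsening has no route to SAE status except discretion. The documents do not support that. Admission and threat to life count whatever the onset, as does an intervention needed to prevent either, and every AE here has already been treated or warrants treatment.

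A reader might further infer that every affected event moves from 24 hours to about six months. That does not hold either. The fast deadlines apply only to unanticipated, study-related SAEs. The unanticipated-problem rules catch some of those, and study researchers see AEs quarterly. Nor are the events hidden from the DSMB: the bi-annual report gives the frequency, type and details of AEs.

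**Conclusion.** The mismatch is real but narrow. It clearly affects a participant with significant disability at enrollment who becomes lastingly more disabled, with treatment given or warranted and with no admission, threat to life or intervention needed to avert one. Such an event is serious only if judged medically important. A mild deficit that becomes disabling is ambiguous, so six sites could grade it differently.

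Reporting speed suffers only for unanticipated, study-related events that are not also unanticipated problems. For anticipated or unrelated events the effect is confined to SAE counts.

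It is tempting to size this by the 900 planned patients, on the ground that nearly all have some impairment at enrollment. That describes who could have such an event, not how many will; it is also an inference from eligibility, not a stated figure. The documents give no basis for an event count, and with this many conditions to satisfy the number is probably small. The conclusion rests on a literal reading of the onset limit. The correction is still worth making because it costs little and removes an avoidable inconsistency in safety grading.

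**What to change.** In the disability outcome of the SAE section, insert *or became significantly worse* after *began*, so that it matches item 2 of the Adverse Event definition. Baseline disability that has not changed would still not qualify. Make the same change in the data and safety monitoring plan wherever it repeats the definition.

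Then re-check AEs recorded as worsened pre-existing conditions against the revised outcome before final safety reporting. Most of the remaining value is here. The milestone schedule puts the end of 12-month follow-up at 10/31/2022, and version 15.0 is dated 01-23-23. Analyses are due 7/15/2023 and results submission 9/30/2023, and a final DSMB report and meeting follow the end of participation.

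The cost is one phrase, a brief record review and possibly slightly more SAEs to report.
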